### Safety

All patients who receive any portion of the intended treatments (TEA or 4Q-TAP) will be included in safety analysis.

Patient demographics, baseline characteristics and medical history will be summarized descriptively by treatment arm. Mean, standard deviation, median, minimum and maximum will be reported for continuous variables. Frequencies and proportions will be reported for categorical variables. An independent samples t-test will be used to evaluate the difference between QoR-15 change scores between treatment arms. Change scores within treatment arms will be summarized using the mean and 95% CIs. Linear regression analysis will be used to assess QoR-15 change scores between treatment arms while adjusting for select covariates of interest.

The association between dichotomous outcomes (dependent variables) and treatment-related factors will be assessed using univariable and multivariable logistic regression. Time-to-event outcomes will be summarized at critical time points using the method of Kaplan-Meier. Kaplan-Meier plots will be used to visualize the time-to-event information. Cox proportional hazards regression will be used to model the time-to-event outcomes using select covariates of interest.

Upon any modifications to the eligibility criteria and with the intention of broadening patient characteristics, for example: by including patients with prior opioid use, we will address this issue by adjusting the treatment effect using a regression model that includes prior opioid use as an indicator variable and assess the relative difference between the unadjusted treatment effect. Moreover, subgroup analyses will be explored even though we anticipate randomization will maintain covariate balance between treatment arms.

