
Study Design
	
This is a randomized controlled trial designed to test efficacy of 4Q-TAP against TEA (routine of care) on quality of recovery 48 hours after CRS-HIPEC surgery. All patients will be enrolled at MD Anderson Cancer Center.

Number of Patients
	
160 patients randomized to the 2 study arms (80 patients per arm)

Sites
	
MD Anderson Cancer Center

Duration of Study	It is expected that this will take up to 36 months.
Duration of Patient Participation	Patients who consented to participate in the study will remain in the study until last planned outcome is collected on postoperative day 30. Patient will have the opportunity to withdraw from the study at any time.
Primary Endpoint Definition	Quality of recovery (QoR) 48 hours after CRS-HIPEC surgery.
Secondary Endpoints	
 
• Postoperative pain 48 hours
 
• The total opioid consumption within 48 hours after surgery
 
• Length of stay
 
• Incidence of adverse events
 
• Incidence of opioid-related adverse events
 
• Postoperative complications and morbidity
 
• QoR on postoperative day 3, 7 10 and 30.
 

Primary Safety Endpoint	All reported adverse events.
Follow-Up Schedule	The study will be considered complete after all randomized patients have had 30 days of follow-up data collection.
Inclusion Criteria	
 
1. Written informed consent;
 
2. 18 years old or older;
 
3. American Society of Anesthesiologists physical status (ASA) 1-3;
 
4. Scheduled surgery: open elective CRS-HIPEC;
 
5. Able to complete the QoR 15 questionnaire;
 
6. Patients scheduled to receive intraoperative chemotherapy;
 

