#### ***D. Data collection and measurements***

**Preoperative data:** Demographic data to be obtained includes height (cm), weight (kg), age (yr), gender, (ASA) physical status, and self-declared ethnicity. Patients will be questioned for social history (tobacco) and medical history to calculate Charlson comorbidity index score. QoR 15 will be obtained before surgery. Pain meds (type, dose and frequency)

The following **intraoperative data** will be obtained from electronic medical records: surgery and anesthesia time, surgery type and extent of resection, intraoperative chemotherapy (type and dose), highest temperature, intraoperative anesthetic and opioid consumption. Blood loss, fluid therapy and urinary output will also be collected at the end of surgical procedure.

The following **postoperative data** will be obtained from electronic medical records: Postoperative opioid consumption, breakthrough pain medication requirements and oxygen requirements in PACU and in nursing floor (first 48 hours postoperatively). QoR score and pain scores will be obtained on postoperative day 1, 2, 3, 5, 7, 10( $\pm$ 1) and 30( $\pm$ 2) days if the patient is still admitted to the hospital. Nausea and vomiting, requirement of antiemetics, pruritus, requirement of antihistaminic medications and requirement of naloxone in PACU and first and second postoperative morning after surgery will be collected. Ambulation time, flatus and bowel movements (first time), constipation, length of stay will be obtained. Incentive spirometry will be measured on postoperative day 1 and 2. Postoperative complications (Clavien-Dindo scale during hospital admission) and perioperative morbidity scores (POMS day 7) will be obtained from medical records and 30 days after surgery. Preoperative and postoperative routine laboratory data results will also be collected from electronic medical records.

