### **Statistical Considerations**

The primary objective of evaluating the impact of 4 quadrants TAP blocks (4Q-TAP) versus Thoracic Epidural Analgesia (TEA - routine care) on the quality of recovery (QoR) will be conducted using total scores on each patient acquired from the QoR-15. The QoR-15, as previously mentioned, is a validated instrument with well-studied psychometric properties used to measure postoperative quality of recovery. The QoR-15 consists of 15 items. All 15 items follow a Likert scale ranging from 0 to 10 (where “0” refers to none of the time [poor] and “10” refers to all of the time [excellent]). A patient’s total score is the sum score across all 15

items (note: the last 5 items are reverse scored). The lowest score a patient can receive is “0” and the highest score is “150”; where higher total scores indicate better quality of recovery. To evaluate the trial changes in QoR-15 total scores will be computed for each treatment arm. The changes will be compared between patients receiving 4Q-TAP Block and patients receiving TEA. Figure 1 illustrates the trial’s development over time. Once a patient is randomized and the preoperative QoR-15 is administered, which takes approximately 2.4 minutes to complete, patients will be provided postoperative QoR-15 approximately 26 hours after surgery (Figure 1: [A]; Stark et al). Within patient changes from baseline will be computed for each treatment arm. These changes will be compared between treatment arms (Figure 1: [B]).

Figure 1: Trial Schema

This randomized trial will be used to determine if 4Q-TAP Block is non-inferior to TEA based on postoperative changes in QoR-15 using a non-inferiority margin of 10 units. According to Stark et al., the reported mean change in QoR-15 before and after surgery is -22 (95%CI: -26 to -18) based on 127 adults. This information allowed us to assume of a common standard deviation of 23 units for the change in QoR-15’s total score pertaining to each treatment arm, which was ultimately used to derive the study’s sample size.

[figure not shown]
The following hypothesis test will be used to evaluate the trial:

$$H_0: \mu_{4Q-TAP\ Block} - \mu_{TEA} \geq 10.0$$

$$H_a: \mu_{4Q-TAP\ Block} - \mu_{TEA} = 0 \text{ (rejecting } H_0 \text{ implies non-inferiority)}$$

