We will use a one-sided t-test test with a significance level of 0.05 and power of 80%. A non-inferiority margin of 10 was considered by assuming an average change in QoR-15 of -25 units in the TEA arm and that the average change in QoR-15 for the 4Q-TAP Block treatment arm would be no greater than -35.

Figure 2: Non-inferiority assessment

These specifications require an approximate sample size of 140 patients as indicated in Table 1. Moreover, an interim analysis will be conducted at after 70 patients are randomized using stopping boundaries provided by the method of Pock and Simon. At the interim, the trial will stop early if  $p < 0.006$  for efficacy and  $p > 0.367$  for futility (East v6).

Table 1: Estimated sample size given projected study parameters

Expected QoR-15 Avg. Change * for Epidural group	Non-inferiority Margin	Power	Alpha (1-sided)	Approx Sample Size
-25	10	80%	5%	140

\*Avg. Change before and after surgery; Assumed SD = 23; A non-inferiority margin of 10 implies the Avg. Change for TAP will be -35 [ie.  $-25 - (-35) = 10$ ]

\*Sample size for the difference of two means using a two sample test (East v6).

The data will be evaluated per protocol for patients contributing analyzable data.

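### QoR-15 is scheduled on seven postoperative days, but the stated primary comparison uses one change score with no missing-data method, so a patient lacking that form drops out even when adjacent-day scores exist

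*Combined protocol and SAP*

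**What the plan says.** **Collection.** Section D (Data collection and measurements) states that "QoR score and pain scores will be obtained on postoperative day 1, 2, 3, 5, 7", and continues to days 10 and 30. That makes seven postoperative occasions plus baseline. The same sentence ends with a condition: "if the patient is still admitted to the hospital". The Study Event Schedule (Table 1), however, lists QoR-15 among the procedures after discharge.

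**Endpoints.** The synopsis defines the primary endpoint as "Quality of recovery (QoR) 48 hours after CRS-HIPEC surgery" and lists as a secondary endpoint "QoR on postoperative day 3, 7 10 and 30". POD 5 appears in no aim or endpoint. Statistical Considerations times the postoperative form differently: "patients will be provided postoperative QoR-15 approximately 26 hours after surgery".

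**Analysis.** The methods for QoR-15 change stand in the Safety section that follows Statistical Considerations: "An independent samples t-test will be used to evaluate the difference between QoR-15 change scores between treatment arms", and "Linear regression analysis will be used to assess QoR-15 change scores between treatment arms while adjusting for select covariates of interest". Neither sentence names a day. Statistical Considerations adds "The data will be evaluated per protocol for patients contributing analyzable data". The later headings for the primary and secondary outcome analyses have no QoR-15 text beneath them. No repeated-measures model, imputation or missing-data sensitivity analysis appears anywhere.

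**The concern.** Both stated methods are cross-sectional: each takes one change score per patient. If the primary form is absent, the patient has no analysable value and leaves the primary comparison. POD 1 and POD 3 scores that carry information about the missing value are not used.

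Two things are at stake. The first is precision, because information already collected is set aside. The second, more important in a non-inferiority trial, is bias. If 4Q-TAP patients who are doing badly miss the form more often than comparable TEA patients, the observed 4Q-TAP mean is too high and the test moves toward declaring non-inferiority. The protocol's background describes different side effects and bedside management for the two techniques, so a difference in missingness is plausible. Nothing in the documents shows that it will occur.

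**Working it through.** **Inputs from the documents.** Margin 10, SD 23, one-sided alpha 0.05, power 80%, 1:1 allocation, required N 140, one interim look after 70 patients (efficacy p < 0.006, futility p > 0.367), 160 randomized.

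**Assumptions.** The documents give neither the share *d* of primary forms missing nor *R²*, the share of variance in the primary change score explained by the other days. The gap between 140 and 160 would fit 12.5% loss, since 140/(1 − 0.125) = 160, but the plan does not say so.

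**Step 1: the plan's own figures.**
- SD from the cited interval: (4/1.96) × √127 = 23.0.
- Fixed-design n per arm: 2 × (1.645 + 0.842)² × 23²/10² = 65.4, so 66 per arm, or 132 in total (134 with the exact t distribution).
- With an O'Brien-Fleming-type look at half the information (spending 0.0056, which rounds to the stated 0.006) and non-binding futility, power is 79.6% at 138 and 80.1% at 140. The stated 140 reproduces.

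**Step 2: precision.** Relative information is 1 − d for complete cases and 1/[(1 − R²)/(1 − d) + R²] for a model using the other days. Power is the fixed-design value Φ(10/(23√(2/n)) − 1.645), with n = 80 × relative information.

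| d | Method | Relative information | n per arm | Power |
|---|---|---|---|---|
| 12.5% | Complete case | 87.5% | 70.0 | 82.3% |
| 12.5% | Model, R² 0.4 | 92.1% | 73.7 | 84.0% |
| 12.5% | Model, R² 0.6 | 94.6% | 75.7 | 84.8% |
| 20% | Complete case | 80.0% | 64.0 | 79.2% |
| 20% | Model, R² 0.4 | 87.0% | 69.6 | 82.1% |
| 20% | Model, R² 0.6 | 90.9% | 72.7 | 83.6% |

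For example, at d = 0.125 and R² = 0.4: 0.6/0.875 + 0.4 = 1.086, and 1/1.086 = 0.921. By the fixed-design formula, complete-case power falls below 80% at about 18% missing (65.4/80 = 0.82). Allowing for the interim look, 140 analysed patients are needed, so the reserve is 12.5%.

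**Step 3: bias, by simulation under stated assumptions.**
- There are 80 patients per arm, SD 23, and a POD 1 to POD 2 correlation of 0.5 or 0.7.
- The true difference (4Q-TAP minus TEA) is −10 on both days, exactly at the margin, and POD 1 is always observed.
- TEA forms at 48 h are missing at random in 15%.
- In 4Q-TAP the log-odds of a missing 48-h form are log(0.15/0.85) − 0.4 − 1.2 × (POD 1 score/23), which averages about 22% missing.
- Each setting has 4,000 trials, one-sided 0.05, no interim look.

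| Correlation | Method | Mean estimate | Non-inferiority declared |
|---|---|---|---|
| 0.5 | Complete-case t-test | −7.5 | 15.4% |
| 0.5 | Estimate using POD 1 | −10.0 | 5.5% |
| 0.7 | Complete-case t-test | −6.5 | 21.9% |
| 0.7 | Estimate using POD 1 | −10.0 | 5.1% |

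The nominal rate is 5%. If the score-dependent mechanism acts in both arms, most of the selection cancels. The t-test's rate is then about 5% to 8% depending on the settings (7.2% and 7.8% with this formula, 8,000 trials).

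**The case against.** A primary endpoint at one time point, compared by a t-test, is legitimate, and collecting scores beyond the named endpoints is not an error. The precision gain is small: about 2 to 3 points of power at 12.5% missing. It shrinks further if patients too ill for the 48-h form also miss POD 1 or POD 3. The bias figures come from an assumed pattern confined mainly to one arm. All of this stands, and it limits the size of the point.

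Objections to a repeated-measures model also stand in part. An unstructured covariance over seven visits has 7 × 8/2 = 28 parameters. Later visits will be incomplete at the interim. If forms are collected only from inpatients, POD 7, 10 and 30 are missing by design after discharge. Discharge probably tracks recovery, so missing-at-random is doubtful for those days. These points argue for limiting the primary model to early days, not for leaving the gap.

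Some stronger readings are tempting but unsupported:
- A reader might infer separate two-sample tests for each secondary day. The plan assigns those days no method, although Study Aims states non-inferiority hypotheses for them.
- A reader might infer that POD 1 is never used. If the 26-hour text governs, the POD 1 score is the primary one and the 48-h score is left out.
- A reader might infer that a patient without the form is lost to the trial. Every treated patient stays in the safety analysis.

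**Conclusion.** The point holds as a gap worth closing, not as a flaw that invalidates the design. The documents establish seven scheduled scores, cross-sectional methods only, restriction to analysable data and no missing-data method. It follows that a missing primary form removes the patient from the primary efficacy result whatever adjacent scores exist.

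The precision cost is modest: about 5 to 7 percentage points of information at 12.5% missing and 7 to 11 at 20%, for R² of 0.4 to 0.6. The more serious exposure is bias. In the assumed scenario it amounts to 2.5 to 3.5 QoR-15 points, a quarter to a third of the margin, with a false non-inferiority rate of 15% to 22%. That result needs missingness that differs by arm and depends on earlier scores. A reader should not take it as a prediction for this trial, because the documents give no missing rate or pattern.

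**What to change.** 1. **Reconcile two texts first.** State whether the primary form is taken at 48 h (synopsis) or about 26 h (Statistical Considerations). State whether later forms are collected from inpatients only (section D) or also after discharge (Study Event Schedule).
2. **Primary analysis.** If 48 h stands, fit a mixed model for repeated measures to the early inpatient scores, at least POD 1, 2 and 3. Include treatment, day, treatment-by-day, baseline QoR-15 and baseline-by-day, with unstructured covariance (6 parameters for three days). Test the 48-h contrast against the 10-unit margin. Use the p-value from the same model at the interim.
3. **Sensitivity analyses.** Keep the change-score t-test. Add a missing-not-at-random analysis, for example one that lowers the imputed 4Q-TAP values step by step until the conclusion changes.
4. **Later days.** Assign a method to each secondary QoR-15 day. Take POD 7, 10 and 30 contrasts from a longitudinal model only if those forms are also collected after discharge. Say what the POD 5 score is for.

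**Cost.** SAP wording and slightly more programming, with no new visits or patients for the primary analysis. The model relies on missing-at-random given the observed scores. Because it adjusts for baseline, its estimate can differ slightly from the change-score t-test even when every form is present.

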## **B. Interventions**

Patients will be randomized 1:1 on the morning of surgery to one of the following 2 interventions:

**TEAgroup:** Patients in this group will be treated as standard of care. An epidural catheter will be placed before induction of anesthesia by an anesthesiologist. The catheter will be placed between the thoracic vertebral spaces 8 and 12 according to routine care. A bolus or infusion of local anesthetic solution with or without the addition opioids will be given before surgical incision according to anesthesia provider's clinical judgment. If deemed appropriate, a pre-incision epidural bolus of hydromorphone (300-800 micrograms) may be administered according to the anesthesia provider's clinical judgment.

**4Q-TAP block group:** Patients in this group will have an ultrasound guided 4Q-TAP block. A maximum of 80 cc of a solution consisting of 30 mg of bupivacaine HCl in 10 cc of PFNS and 65 mg of liposomal bupivacaine in 10 cc of PFNS will be injected before surgical incision in each of the four quadrants.

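### Prior opioid use is a named covariate only if eligibility is widened, yet the criteria already admit such patients, and the QoR-15 comparison is an unadjusted t-test on change

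*Combined protocol and SAP*

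**What the plan says.** The relevant text is in the Safety subsection of Statistical Considerations, where most of the planned models stand.

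- **Conditional adjustment.** If the eligibility criteria are modified to broaden the population, "for example: by including patients with prior opioid use, we will address this issue by adjusting the treatment effect using a regression model". The model would carry prior opioid use as an indicator, and its result would be set against the unadjusted effect.
- **Unconditional analyses.** The same subsection compares QoR-15 change scores between arms with an independent samples t-test. It also plans a linear regression of the change scores on covariates that it does not name, logistic and Cox models (again without named covariates), and exploratory subgroups.
- **Eligibility.** Setting and Population (section A) lists six inclusion and five exclusion criteria, and the synopsis lists the same items. None requires opioid-naive patients and none excludes opioid users.
- **Data.** The preoperative items in Data collection and measurements (section D) include "Pain meds (type, dose and frequency"), and the QoR-15 is obtained before surgery.
- **Design figures.** "We will use a one-sided t-test test with a significance level of 0.05 and power of 80"%, applied to "postoperative changes in QoR-15 using a non-inferiority margin of 10 units".

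**The concern.** The condition does not fit the plan's own criteria. Its example of a broadening is the admission of patients who can already be enrolled. Read literally, the one adjustment that names a covariate waits for an event that need not happen, while the patients who prompted it may be in the trial from the start.

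The general regression does not close the gap, because it leaves its covariates open. Whether prior opioid use or baseline QoR-15 enters could be decided after the data are seen. In a single-blinded non-inferiority trial analysed per protocol, that choice is better settled in advance.

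Two things are at stake: precision in the QoR-15 comparison, and prespecification. The second applies also to 48-hour opioid consumption, a secondary endpoint to which prior opioid use is plausibly related and for which no model is given.

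**Working it through.** **1. Inputs from the plan.** Margin 10 on QoR-15 change; the plan says its source data allowed it to "assume of a common standard deviation of 23 units for the change in QoR-15’s total score"; one-sided alpha 0.05; power 80%; "Patients will be randomized 1:1 on the morning of surgery"; one interim look at 70 patients, at which "the trial will stop early if $p < 0.006$ for efficacy and $p > 0.367$ for futility (East v6"). The stated result is: "These specifications require an approximate sample size of 140 patients as indicated in Table 1". The SD agrees with the interval that the plan cites (half-width 4, 127 adults): 4 × √127 / 1.96 = 23.0.

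**2. Reproducing 140.** A fixed design needs 2 × (1.645 + 0.842)² × 23² / 10² = 65.4, so 66 per arm or 132 in total. The t-test version needs 67 per arm, 134 in total. Neither is 140. A two-look design with the stated interim bounds (z = 2.512 for efficacy, 0.340 for futility), half the information at the interim, and the final bound solved for total alpha 0.05 gives N = 139.6 with non-binding futility and 136.4 with binding futility. The figure of 140 therefore reproduces as a group-sequential size, and this point does not dispute it.

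**3. Unadjusted power at 140.** The expected z at a look with N patients is 10 / (SD × √(4/N)). With SD 23 this is 1.819 at 70 patients and 2.572 at 140. With the stated interim bounds and a final test at one-sided p < 0.05 (an assumption, since the plan gives no final bound), power is 80.5%.

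**4. Power after adjusting for prior opioid use alone.** The residual SD is 23 × √(1 − r²), where r is the correlation of the covariate with the outcome. The documents give no r, so a range is assumed. The equivalent sample size is 140 / (1 − r²).

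| Assumed r | Residual SD | Power at 140 | Equivalent N |
|---|---|---|---|
| 0 | 23.00 | 80.5% | 140 |
| 0.1 | 22.88 | 80.9% | 141 |
| 0.2 | 22.54 | 81.9% | 146 |
| 0.3 | 21.94 | 83.6% | 154 |

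If the final bound is solved for total alpha 0.05 instead, power runs from 80.1% (r = 0) to 83.3% (r = 0.3) with non-binding futility, and from 80.9% to 84.0% with binding futility. The gain is about the same.

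**5. Is r = 0.3 plausible for a yes/no covariate?** With prevalence p and a user/non-user difference D in QoR-15 change, r = D × √(p(1 − p)) / 23. So r = 0.3 needs D = 6.9 / √(p(1 − p)): 23 units at an assumed prevalence of 10%, 17 at 20%, 15 at 30%, and never less than 13.8 (at 50%). Each exceeds the 10-unit margin.

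**6. The same question from prevalence and difference.** For assumed p of 10–30% and D of 5–15 units, R² = p(1 − p)D² / 23² runs from 0.004 to 0.089. In a fixed-design approximation at 140, power moves from 82.3% to between 82.5% and 85.3%, a gain of about 0.1 to 3.0 percentage points.

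**7. Chance imbalance.** Under the same assumptions, an imbalance of 1.96 standard errors shifts the arm difference by 1.96 × D × √(p(1 − p) × 4/140). That is 0.5 units (p = 10%, D = 5) to 2.3 units (p = 30%, D = 15), at most 23% of the margin.

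The gain from baseline QoR-15 was not calculated. It needs the correlation of baseline with change, which the documents do not give.

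**The case against.** A reader might infer that prior opioid use would never be used in any analysis. The documents do not support that. The unconditional regression and the exploratory subgroups could both include it. The trigger covers any broadening, with opioid use only as an example. The documents also do not show whether an earlier version of the criteria excluded opioid users; if one did, the condition may already be met.

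A reader might also infer that the unadjusted comparison is biased. It is not. Under 1:1 randomization the t-test's error rate already allows for chance imbalance, and the shifts in step 7 are part of the variation that the SD of 23 describes.

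Three further objections carry weight. The plan does not call prior opioid use prognostic: the promised model compares adjusted and unadjusted effects after a change in eligibility, and no data link the variable to QoR-15 change. The gain is small, from a base already at the 80% target, and r = 0.3 is demanding. With baseline QoR-15 also in the model, the relevant quantity is the partial correlation of opioid use given baseline, which is unknown.

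All of this limits the size of the point. It does not remove the mismatch between the condition and the criteria, or the absence of any named covariate in the unconditional models.

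**Conclusion.** The point holds as one of precision and prespecification. The only adjustment naming prior opioid use is tied to a broadening of eligibility that the current criteria make unnecessary, and neither that variable nor baseline QoR-15 is prespecified in an unconditional model. For prior opioid use alone the benefit is about 0.4 to 3.1 percentage points of power at 140 patients, with the lower part of that range more likely for a yes/no covariate. This rests on assumed correlations of 0.1 to 0.3 and a final test at one-sided 0.05. No figure can be given for baseline QoR-15 or for opioid consumption. The validity of the planned t-test and the sample size of 140 are unaffected. The change is worth making because it uses data already collected and closes a modelling choice that is now open.

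**What to change.** - Remove the eligibility condition from the prior-opioid sentence.
- Make the QoR-15 comparison a linear model of the change score with treatment, baseline QoR-15 and prior opioid use (yes/no). Assess the upper or lower confidence limit for the treatment effect against the 10-unit margin, with the same model at the interim and final analyses. Keep the unadjusted t-test as a sensitivity analysis.
- Derive prior opioid use from the preoperative pain-medication record, with a short written definition that includes a look-back period, since the plan gives none.
- Use prior opioid use as a covariate in the comparison of 48-hour opioid consumption.

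Cost: a definition of prior opioid use and a model for opioid consumption must be written, so this is somewhat more than a one-sentence edit. No new data are needed and the sample size does not change.
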